10.7 Handling of Missing Data

As all treatments are scheduled in a single study visit, the level of missing data for the primary endpoint is anticipated to be small. Every attempt will be made to avoid missing data. All subjects will be used in the safety analysis, using nonmissing data available. No imputation process will be used to estimate/substitute missing data.

10.8 Determination of Sample Size

Each of the expected 36 completed subjects will receive 1 dose of NH002 (with 12 subjects per NH002 cohort). As this is a dose finding study, a formal sample size calculation was not required. The number of subjects dosed within each cohort is based on safety, with the objective of exposing the lowest possible number of subjects to the investigational agent, while still being able to assess safety.

10.9 Protocol Deviations

Major protocol deviations will be defined in the statistical analysis plan and agreed upon during a Data Review Meeting prior to database lock.

11 QUALITY ASSURANCE AND QUALITY CONTROL

11.1 Audit and Inspection

Study centers and study documentation may be subject to Quality Assurance audit during the course of the study by the sponsor or its nominated representative. In addition, inspections may be conducted by regulatory authorities at their discretion.

11.2 Monitoring

Data for each subject will be recorded on a CRF. Data collection must be completed for each subject who signs an ICF and is administered study agent.

In accordance with current good clinical practice (cGCP) and International Council for Harmonisation (ICH) guidelines, the study monitor will carry out source document verification at regular intervals to ensure that the data collected in the CRF are accurate and reliable.

The investigator must permit the monitor, the IEC/IRB, the sponsor's internal auditors, and representatives from regulatory authorities direct access to all study-related documents and pertinent hospital or medical records for confirmation of data contained within the CRFs.

11.3 Data Management and Coding

The sponsor and/or the appointed representative(s) will be responsible for activities associated with the data management of this study. This will include setting up a relevant database and data transfer mechanisms, along with appropriate validation of data and resolution of queries. Data generated within this clinical study will be handled according to the relevant standard operating procedures of the data management and biostatistics departments of the sponsor and/or the appointed representative(s).

Study centers will complete the CRF. Data entered into the CRF must be verifiable against source documents at the study center. Data to be recorded directly on the CRF will be identified and the CRF will be considered the source document. Any changes to the data entered into the data capture system will be recorded in the audit trail (and if electronic, will be FDA CFR 21 Part 11 compliant).

Medical coding will use Medical Dictionary for Regulatory Activities for concomitant diseases and AEs and WHODrug for medications.

Missing or inconsistent data will be queried in writing to the investigator for clarification. Subsequent modifications to the database will be documented.

11.4 Quality Management and Risk Evaluation

Details are provided in [Section 7.3.2](#).

12 RECORDS AND SUPPLIES

12.1 Drug Accountability

On receipt of the study agent (including rescue medication, if relevant), the investigator (or designee) will conduct an inventory of the supplies and verify that study agent supplies are received intact and in the correct amounts before completing a supplies receipt. The investigator will retain a copy of this receipt at the study center and return the original receipt to the study monitor. The monitor may check the study supplies at each study center at any time during the study.

It is the responsibility of the study monitor to ensure that the investigator (or designee) has correctly documented the amount of the study agent received, dispensed, and returned on the dispensing log that will be provided. A full drug accountability log will be maintained at the study center at all times. The study monitor will arrange collection of unused study agent returned by the subject. The study monitor will also perform an inventory of study agent at the close-out visit to the study center. All discrepancies must be accounted for and documented.

12.2 Financing and Insurance

Financing and insurance of this study will be outlined in a separate agreement between the contract research organization and the sponsor.

13 ETHICS

13.1 Independent Ethics Committee or Institutional Review Board

Before initiation of the study at each study center, the protocol, the ICF, other written material given to the subjects, and any other relevant study documentation will be submitted to the appropriate IEC/IRB. Written approval of the study and all relevant study information must be obtained before the study center can be initiated or the study agent is released to the investigator. Any necessary extensions or renewals of IEC/IRB approval must be obtained for changes to the study such as amendments to the protocol, the ICF or other study documentation. The written approval of the IEC/IRB together with the approved ICF must be filed in the study files.

The investigator will report promptly to the IEC/IRB any new information that may adversely affect the safety of the subjects or the conduct of the study. The investigator will submit written summaries of the study status to the IEC/IRB as required. On completion of the study, the IEC/IRB will be notified that the study has ended.

13.2 Regulatory Authorities

Relevant study documentation will be submitted to the regulatory authorities of the participating countries, according to local/national requirements, for review and approval before the beginning of the study. On completion of the study, the regulatory authorities will be notified that the study has ended.

13.3 Ethical Conduct of the Study

The investigator(s) and all parties involved in this study should conduct the study in adherence to the ethical principles based on the Declaration of Helsinki, cGCP, ICH guidelines, and the applicable national and local laws and regulatory requirements.

13.4 Informed Consent

The process of obtaining informed consent must be in accordance with applicable regulatory requirement(s) and must adhere to cGCP.

The investigator is responsible for ensuring that no subject undergoes any study related examination or activity before that subject has given written informed consent to participate in the study.

The investigator or designated personnel will inform the subject of the objectives, methods, anticipated benefits and potential risks and inconveniences of the study. The subject should be given every opportunity to ask for clarification of any points s/he does not understand and, if necessary, ask for more information. At the end of the interview, the subject will be given ample time to consider the study. Subjects will be required to sign and date the ICF. After signatures are obtained, the ICF will be kept and archived by the investigator in the investigator's study file. A signed and dated copy of the subject ICF will be provided to the subject or their authorized representative.

It should be emphasized that the subject may refuse to enter the study or to withdraw from the study at any time, without consequences for their further care or penalty or loss of benefits to which the subject is otherwise entitled. Subjects who refuse to give or who withdraw written informed consent should not be included or continue in the study.

If new information becomes available that may be relevant to the subject's willingness to continue participation in the study, a new ICF will be approved by the IEC(s)/IRB(s) (and regulatory authorities, if required). The study subjects will be informed about this new information and reconsent will be obtained.

13.5 Subject Confidentiality

Monitors, auditors, and other authorized agents of the sponsor and/or its designee, the IEC(s)/IRB(s) approving this research, and the United States (US) FDA, as well as that of any other applicable agency(ies), will be granted direct access to the study subjects' original medical records for verification of clinical study procedures and/or data, without violating the confidentiality of the subjects to the extent permitted by the law and regulations. In any presentations of the results of this study or in publications, the subjects' identity will remain confidential.

All personal data collected and processed for the purposes of this study should be managed by the investigator and his/her staff with adequate precautions to ensure confidentiality of those data, and in accordance with the HIPAA,²¹ applicable to national and/or local laws and regulations on personal data protection.

14 REPORTING AND PUBLICATION, INCLUDING ARCHIVING

Essential documents are those documents that individually and collectively permit evaluation of the study and quality of the data produced. After completion of the study (end of study defined as the date of the last visit of the last subject), all documents and data relating to the study will be kept in an orderly manner by the investigator in a secure study file. This file will be available for inspection by the sponsor or its representatives. Essential documents should be retained for 2 years after the final marketing approval in an ICH region or for at least 2 years since the discontinuation of clinical development of the investigational product. It is the responsibility of the sponsor to inform the study center when these documents no longer need to be retained. The investigator must contact the sponsor before destroying any study related documentation. In addition, all subject medical records and other source documentation will be kept for the maximum time permitted by the hospital, institution, or medical practice.

The sponsor must review and approve any results of the study or abstracts for professional meetings prepared by the investigator(s). Published data must not compromise the objectives of the study. Data from individual study centers in multicenter studies must not be published separately.

16 APPENDICES

16.1 Image Evaluation Guidelines

Sponsor-recommended equipment/platforms:*

| | |
|----------------------------|-----------------------------------|
| Ultrasound System | [REDACTED] with contrast LVO mode |
| Video Recording Instrument | [REDACTED] |
| Image Evaluation Software | Windows Media Player/DICOM viewer |

**Equipment other than the listed can be used after discussion and approval by the sponsor.*

Equipment technical settings to be used at each site: Site should follow standard institutional guideline(s) for equipment technical settings and subject preparation, positioning, and overall comfort measures.

Site qualification process: Local site imaging technicians must be trained and qualified in equipment operation, including the ability to identify faulty or unacceptable images and understand the importance of repeating imaging when appropriate. (In the event of faulty or unacceptable images, an unscheduled visit can be scheduled to repeat all necessary procedures.)

Acquisition quality control monitoring process:

A checklist will be used for quality control. Checklist for each treatment:

- Subject ID and treatment number were input correctly on ultrasound imaging system and external video recorder
- Investigator confirmed settings of mechanical index, depth, focal depth, dynamic range, gain, and time gain compensation were optimized for each subject
- 4-chamber view of pre-injection B mode acquired
- 2-chamber view of pre-injection B mode acquired
- 4-chamber view of pre-injection contrast mode acquired
- 2-chamber view of pre-injection contrast mode acquired
- Treatment administered
- 4-chamber view of post-injection contrast mode acquired
- 2-chamber view of post-injection contrast mode acquired
- 19 transitions between 2-chamber and 4-chamber view post-injection. Two or less transitions may be skipped when a standard 12-lead ECG is conditionally triggered during the imaging session.
- A video containing consecutive pre-injection and 10-minute post-injection sessions acquired
- 4 pre-injection DICOM cineloop sequences acquired
- 20 post-injection DICOM cineloop sequences acquired (including 10 DICOM cineloop sequences of 4-chamber view and 10 DICOM cineloop sequences of 2-chamber view). Two or less sequences may be skipped when a standard 12-lead ECG is conditionally triggered during the imaging session.)

[figure not shown]
Data storage and transfer:

USB flash disks or CD(s) labeled with subject ID will be used to store and transfer video files and DICOM files acquired in the study. Each subject's image data will be stored in one USB flash disk or CD(s) and shipped to the sponsor or designated contract research organization for randomized sequencing (for central blinded reviews).

Standards for Image Evaluation:**(a) LVO:**

- 0 = none (no visible contrast within the LV cavity);
- 1 = faint (weak or trace effect of contrast within the LV cavity);
- 2 = moderate (some areas of the LV cavity fully opacified but without a time when the whole cavity was filled with contrast to the same high density);
- 3 = complete (homogeneous and high intensity effect).

(b) LVEBD: The apical 4-chamber and 2-chamber views of the left ventricle were divided into segments by using cardiac maps. A total delineation score (0-24) was obtained by adding the scores (0 = inadequate, ie, border not visible; +1 = sufficient, ie, border barely visible; +2 = good, ie, border clearly visible) from the six individual segments in each of the two views.

- 0 = inadequate, ie, border not visible;
- 1 = sufficient, ie, border barely visible;
- 2 = good, ie, border clearly visible.

Image display sequence and randomization.

The sponsor or designated contract research organization will merge the grouped images obtained in the study from each subject and present the merged set to the blinded reader in a random sequence. The whole recorded image data will be used for scoring by the blinded reader(s). The blinded reader(s) should document the time points of the best images used for LVEBD scoring as well as the start and end time points of useful contrast imaging.

Central blinded reader training and qualification:

Central blinded reader(s) have been selected to assess the echocardiographic images for this study because of their background training and qualifications. These selected blinded central reader(s) will also be trained in scoring procedures for LVO and LVEBD using sample images, prior to the central image evaluations.

Timing of image reads and the read process:

Merged/randomized image scoring of blinded central reader(s) will be done after all the images in the study are obtained.

Imaging data lock process:

Each blinded evaluation will be locked in the dataset shortly after it is obtained and before additional types of image evaluations are performed.

If indicated and applicable, consensus image evaluations (or consensus reads) can be performed after the individual readings (if applicable) are completed and locked. (These consensus reads will NOT serve as the primary image evaluation used to demonstrate any preliminary efficacy of NH002.) If used, the consensus reads will also be locked once obtained and before additional types of blinded readings are performed.

Quality control of the image display and blinded interpretation process:

Central image evaluations will occur offsite to ensure that the blinded reader(s) perform their image evaluations independently of other image evaluations. The blinded central reader(s) will not have any knowledge of subject identifiers nor dose level received to obtain an image. The blinded central reader(s) will also evaluate image groups in a randomized sequence.

Imaging data transfer process to the sponsor:

All USB flash disks or CDs with subject data will be returned to the sponsor or designated contract research organization after the completion of study (from both the local sites and the blinded central reader[s]).

Archiving of images and blind image interpretations:

Images and blind image interpretations will be archived in the sponsor or designated contract research organization's database.

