7 INVESTIGATIONAL PLAN

7.1 Overall Study Design and Plan: Description

This is a phase 1, multicenter, open-label clinical study to evaluate the safety and tolerability of 3 ascending doses of NH002. Up to 36 eligible subjects will be enrolled with sequential allocation to 1 of 3 cohorts with the following IV doses of NH002: 2.5 μ l/kg, 5.0 μ l/kg, or 10.0 μ l/kg. Each patient will undergo an unenhanced ultrasound examination and a NH002 contrast-enhanced examination on the same day at Day 1. Subjects will remain at the clinical site for up to 240 minutes of observation after NH002 administration.

All AEs will be evaluated during the successive cohorts of subjects, per dose level. In general, enrollment will be halted and safety data reviewed for termination or continuation with the occurrence of any SAE considered at least possibly related to study agent administration (in any 1 subject) or clinically significant toxicity listed in [Section 7.5.1.2](#) in 30% of subjects (within any 1 of the 3 dose levels). Please see [Section 7.5.1.2](#) for details on treatment stopping criteria for this trial.

There will be a screening period (28 days before NH002 administration), a dosing period (during Day 1) that will include a single dose administration of NH002, and a 7-day follow-up period for each cohort. Continuous echocardiographic imaging will be performed at specified time points before, during, and after dose administration. The contrast agent will be prepared and administered by designated pharmacy technician(s), study nurse(s), sonographer, or radiologist. Subjects will be observed at a clinical site for at least 240 minutes (4 hours) and evaluated for AEs. Subjects will be contacted by phone after the end of treatment at 72 hours (ie, Day 4 [+3]) and at Day 7 (+3), for a follow-up safety assessment. Any drug-related AE or SAE will be followed until resolution.

High ultrasound mechanical index (MI) values may cause microsphere cavitation or rupture and lead to ventricular arrhythmias. Additionally, end-systolic triggering with high MIs has been reported to cause ventricular arrhythmias. The safety of NH002 at MIs greater than 0.8 will not be evaluated.

In accordance with protocol guidelines for imaging, each study center will follow standard practice for (transthoracic) echocardiographic imaging, pre- and post-dosing. Efficacy evaluations will be based on blinded central echocardiographic imaging assessments.

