DICOM cineloop sequences will be stored. Each cineloop sequence will be acquired for a duration of 5 seconds whenever the imaging mode or the imaging view is changed. [REDACTED]

[See Figure 5](#) for details.

Figure 5: Imaging Guidelines

Each subject should have 24 DICOM file(s) for the NH002 dosing and the unenhanced imaging. These files will be exported to the USB flash drive or CD from the ultrasound machine.

The video for NH002 dosing will be recorded by an external video recorder in mp4 format. The sponsor will provide each site with a recording instrument confirmed to be compatible with [REDACTED]. All clinical sites will use the same model of the recording instruments. The recording duration will be at least 15 minutes for each dosing period (starting from approximately 5 minutes before

and continuing until 10 minutes after dosing). Each subject should have at least 1 video file stored in a USB flash drive or CD (for the NH002 dosing and the unenhanced ultrasound imaging). The sponsor will also provide USB flash drives or CDs to sites.

Central image evaluations will occur offsite to ensure that the blinded reader(s) perform their image evaluations independently. The blinded central reader(s) will not have any knowledge of subject identifiers nor dose level received to obtain an image. DICOM image groups obtained in each subject will be merged and presented to the blinded reader(s) in a random sequence. Each blinded evaluation will be locked in the dataset shortly after it is obtained and before additional types of image evaluations are performed, if indicated *and applicable*.

If indicated *and applicable*, consensus image evaluations (or consensus reads) can be performed after the individual readings (if applicable) are completed and locked. (These consensus reads will NOT serve as the primary image evaluation used to demonstrate any preliminary efficacy of NH002.) **If used**, the consensus reads will also be locked once obtained and before additional types of blinded readings are performed.

The blinded central reviewer(s) with appropriate training, education, and qualifications will assess the echocardiographic images for this study. The blinded central reader(s) will be provided with redacted USB flash drive(s) or CD(s) in order to access and score randomized video image groups without knowledge/information of dosing or subject identifiers. Refer to [Image Evaluation Guidelines](#) for more information.

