- Table 13.1.2.1: Summary of LVEBD Score, Per Protocol Set
- Figure 13.1.2.2: LVEBD Score, Per Protocol Set
- Figure 13.1.2.3: Change of LVEBD Score, Per Protocol Set
- Table 13.2.1.1: Summary of LVEBD Score for Subjects with Suboptimal LVEBD at Baseline (as defined by 2 or more contiguous segments of 6 segments that cannot be visualized reliably in either the apical 4- and/or the 2-chamber view), Full Analysis Set
- Figure 13.2.1.2: LVEBD Score for Subjects with Suboptimal LVEBD at Baseline (as defined by 2 or more contiguous segments of 6 segments that cannot be visualized reliably in either the apical 4- and/or the 2-chamber view), Full Analysis Set
- Figure 13.2.1.3: LVEBD Score for Subjects with Suboptimal LVEBD at Baseline (as defined by 2 or more contiguous segments of 6 segments that cannot be visualized reliably in either the apical 4- and/or the 2-chamber view), Full Analysis Set
- Table 13.2.2.1: Summary of LVEBD Score for Subjects with Suboptimal LVEBD at Baseline (as defined by 2 or more contiguous segments of 6 segments that cannot be visualized reliably in either the apical 4- and/or the 2-chamber view), Per Protocol Set
- Figure 13.2.2.2: LVEBD Score for Subjects with Suboptimal LVEBD at Baseline (as defined by 2 or more contiguous segments of 6 segments that cannot be visualized reliably in either the apical 4- and/or the 2-chamber view), Per Protocol Set
- Figure 13.2.2.3: LVEBD Score for Subjects with Suboptimal LVEBD at Baseline (as defined by 2 or more contiguous segments of 6 segments that cannot be visualized reliably in either the apical 4- and/or the 2-chamber view), Per Protocol Set
- Listing 06.2: Image Evaluation - LVEBD Score, Safety Set
- Duration of Clinically Useful Contrast Enhancement

The duration of clinically useful contrast enhancement is the number of minutes between start time point and end time point of useful contrast imaging, rounded to one decimal place.

The formula for duration calculation is as below.

Duration (Minutes)=(End Time (hh:mm:ss) of Useful Contrast Imaging - Start Time (hh:mm:ss) of Useful Contrast Imaging)/60, rounded to one decimal place.

The descriptive statistics (n, mean, standard deviation, median, minimum, maximum, and 95% CI) of the duration of clinically useful contrast enhancement will be presented by each dose group and overall. The unit of duration is minute.

Furthermore, the boxplots of duration of clinically useful contrast enhancement will be presented by each cohort and overall.

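### Baseline LVEBD is not read separately from, or locked before, the same subject's enhanced images, which can bias the two LVEBD change endpoints

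*Protocol*

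**What the plan says.** Three parts of the plan bear on this.

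- **Recording.** The site checklist in Protocol 16.1 asks for "A video containing consecutive pre-injection and 10-minute post-injection sessions acquired". Protocol 7.1.1 adds "The recording duration will be at least 15 minutes for each dosing period", from about 5 minutes before dosing to 10 minutes after. Separately, each subject has 24 DICOM loops, 4 before injection (two views in two imaging modes) and 20 after.
- **Display and scoring.** Under 16.1, each subject's images are merged and the merged material is shown in random order. Then: "The whole recorded image data will be used for scoring by the blinded reader(s". The reader also chooses frames: "The blinded reader(s) should document the time points of the best images used for LVEBD scoring". Protocol 7.1.1 has readers "score randomized video image groups without knowledge/information of dosing or subject identifiers".
- **Locking.** Protocol 7.1.1 and 16.1 lock each blinded evaluation soon after it is made and before any further type of evaluation begins. Neither section makes the baseline read an evaluation of its own.

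The affected endpoints are the change in LVEBD score in all subjects, and the same change in subjects with suboptimal LVEBD at baseline (Protocol 6.4 and 10.5.2; SAP 5.4.1.1). Both are to be assessed by the blinded central reader. SAP 7.2.2, however, has the suboptimal classification transferred by the sponsor, apart from the reader's scores.

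**The concern.** LVEBD is a judgement of 0, 1 or 2 for each segment. A reader who has just seen where the border lies under contrast is no longer judging the unenhanced image on its own. The border may then look worse by comparison, or be easier to trace. The same knowledge can influence which unenhanced frame is picked as best.

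The randomisation described is of image groups across subjects. It does not separate before from after within a subject. SAP 1.3 confirms that there is no placebo or active control, so no parallel group would reveal or cancel a shift in baseline scores. At stake is whether the reported LVEBD change measures the agent's effect alone or also contains an effect of how the images were read.

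**Working it through.** The plan gives no figure for this bias, so there is none to reproduce. The check is of the text, followed by what a given shift would do.

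**1. The plan's own counts agree.**
- Post-injection loops: 10 min × 60 / 30 s = 20.
- All loops: 4 + 20 = 24.
- Video: 5 + 10 = 15 minutes.
- LVEBD maximum: 12 segments × 2 = 24.

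The four pre-injection loops are therefore files of their own and can be shown separately without new imaging.

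**2. Could baseline be protected by another provision?**
- Random order: it acts on merged image groups, so it leaves a subject's two sessions together.
- Lock rule: it would work if baseline were a separate evaluation, but no section says so.
- SAP 5.4.1.2: it has LVO graded from a pair of views in each session, but gives no order of reading and says nothing about separate LVEBD reads.
- Masking: it concerns dose and subject identity, not timing.

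None of these requires a baseline score before the enhanced images are seen.

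**3. Effect of a shift.** Let B be the baseline score read without sight of enhancement, P the post-injection score, and s the shift in baseline caused by seeing it.
- Observed change = P − (B + s) = (P − B) − s.
- If k segments move down one grade, s = −k and the change rises by k. If k segments move up one grade, the change falls by k.

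| k (assumed) | Shift in change, points | Share of the 24-point scale |
|---|---|---|
| 0 | 0 | 0% |
| 1 | +1 or −1 | 1/24 = 4.2% |
| 2 | +2 or −2 | 2/24 = 8.3% |

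The documents give no value of k and no sign.

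**4. Between doses.** The difference between two doses is altered by −(s_high − s_low). A shift that is the same at every dose cancels. Only a shift that differs by dose would distort the comparison.

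**5. Suboptimal subgroup.** Entry needs at least two adjoining segments of the six in one view that cannot be seen reliably. The plan does not map this to a grade. If it means grade 0 (assumption), segments moving from 1 to 0 can bring a subject in, provided they are adjoining and in the same view; a move from 2 to 1 cannot. Two shifted segments therefore do not by themselves create a suboptimal subject.

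**6. Endpoints outside this route.** The two LVO percentages and the duration of useful contrast are not changes from baseline. Grade 0 for LVO means that no contrast is visible, which leaves little room for judgement before injection.

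**The case against.** The best defence is that the plan never promises a reader masked to timing. Blinded here means blinded to dose and identity, and visible contrast would reveal an enhanced image whatever was done. That is correct, so it would be wrong to say that a pre/post blind has failed. The point is narrower: the order of reading and locking. Readers would still recognise a baseline set as baseline, but would not yet have seen the same heart enhanced.

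It is also fair that separate loops exist, that the direction is unknown, that the endpoints are descriptive and secondary, and that the suboptimal flag may not come from the reader at all. These limit the size of the point but do not remove it.

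A reader might go further and infer that the dose blind is insecure. Protocol 7.1 states "Up to 36 eligible subjects will be enrolled with sequential allocation to 1 of 3 cohorts", so acquisition date follows dose, and the site checklist includes "Subject ID and treatment number were input correctly on ultrasound imaging system and external video recorder". If dates were visible, sorting 36 subjects into three blocks of 12 would recover every dose. The documents do not support that premise. Readers are to have no knowledge of dose, receive redacted media, and read offsite in random order after all imaging is complete. The checklist item is a check at acquisition, before files go for central sequencing. The SAP's "Start Time (hh:mm:ss) of Useful Contrast Imaging" does not say whether clock or elapsed time is meant. No text shows dates reaching the reader. At most, the redacted fields could be listed.

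**Conclusion.** The point holds as a cheap improvement. The plan lets baseline LVEBD be graded with the same subject's enhanced borders already seen, and no rule locks it first. The two LVEBD change endpoints are exposed. The suboptimal classification is exposed only if the central reader makes it, which Protocol 6.4 and SAP 7.2.2 leave unsettled between them.

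The size is unknown: one point of change per segment moved by one grade, in either direction. Any specific figure, such as 2 points, is an assumption. A shift common to all doses would affect the reported change at each dose but not the comparison between doses. The primary safety endpoint is unaffected. Central reading follows all imaging, so it cannot influence escalation decisions.

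**What to change.** In Protocol 7.1.1 and 16.1:

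1. Present the 4 pre-injection loops of all subjects first, as their own randomised set. If the pre-injection part of the video is also wanted for scoring, cut it at the injection and include it here.
2. Have the central reader score baseline LVEBD and the suboptimal flag, and lock both under the existing lock rule. The pre-injection LVO grade that the SAP needs can be entered in the same session.
3. Only then release the post-injection loops and the post-injection part of the video, in a new random order under a new code. Duration of useful contrast needs only this part.
4. Align SAP 7.2.2, so that the suboptimal flag comes from the locked central read.

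As a clarification only, state that the existing redaction covers acquisition date and clock time, and that image times are recorded as elapsed time from injection.

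**Cost:** two reading sessions instead of one, and somewhat more file preparation for the party that already sequences the images. Readers, images and subjects are unchanged.
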